7.13.8 Fundus Photography

Part I and Part II

Presence and severities (none, mild, moderate, severe) of retinal pigment epithelium (RPE) hyperplasia, retinal arteriolar narrowing, retinal vessel sheathing, optic atrophy/pallor and optic disc swelling and presence of targeted ocular findings (TOF) will be analyzed.

The shift of fundus photograph will be summarized from "none", "mild", "moderate", "severe" at baseline to "none", "mild", "moderate", "severe" at any post baseline visit.

7.13.9 Vital Signs

Part I and Part II

For systolic blood pressure, diastolic blood pressure and heart rate, their observed values and change from baseline will be summarized by treatment groups and visits.

7.13.10 Laboratory Assessments

7.13.10.1 Safety Assessments

Part I and Part II

For the purposes of summarization in both the tables and listings, all laboratory values will be converted to standardized units. Laboratory abnormalities will be graded using the Common Terminology Criteria for Adverse Events (CTCAE) version 4.0. For numeric laboratory parameters the observed lab values and mean change from baseline will be summarized at each visit. Clinically significant laboratory data will be summarized using shift tables where appropriate. For each subject, the lab values in hematology and blood chemistry will be flagged as "low", "normal", or "high" relative to the normal ranges of the central laboratory, or as "unknown" if no result is available.

For blood chemistry and serum chemistry, shifts tables from baseline to low/high postbaseline will be presented. Shift to low includes normal to low, high to low, and unknown to low. Shift to high includes normal to high, low to high, and unknown to high. For a subject if a lab is collected multiple times at post baseline, as long as one lab value is low this subject is regarded to have "low" post-baseline for this lab parameter. Similarly, if at least one postbaseline lab value is "high" this subject is regarded to have "high" post-baseline for this lab parameter.

Markedly abnormal indicate clinically significant laboratory abnormalities determined by Biogen. For hematology and blood chemistry the number and percentage of subjects with markedly abnormal laboratory post-baseline will be summarized by treatment group in Part I and Part II following the criteria in Table 2. Shifts tables from baseline to markedly abnormal post-baseline will also be summarized. For a subject if a lab is collected multiple times at post baseline, as long as one lab value is markedly abnormal this subject is counted to be markedly abnormal for this lab parameter.

Listings of subject's laboratory data for each visit will be presented.

| Parameter name | Unit | Low | High | | | |
|-------------------------------------|---------------------------|--------------|---------------|--|--|--|
| Hematology | | | | | | |
| White blood cells | x10 ⁹ cells/L | <3.0 | >16 | | | |
| Lymphocytes | x10 ⁹ cells/L | <0.8 | >12 | | | |
| Neutrophils | x10 ⁹ cells/L | <1.5 | >13.5 | | | |
| Monocytes | x10 ⁹ cells/L | N/A | >2.5 | | | |
| Eosinophils | x10 ⁹ cells/L | N/A | >1.6 | | | |
| Basophils | x10 ⁹ cells/L | N/A | >1.6 | | | |
| Red blood cells (RBC) | x10 ¹² cells/L | ≤ 3.5 | ≥ 6.4 | | | |
| Hemoglobin - Females | - / T | ≤ 9 5 | ≥175 | | | |
| - Males | g/L | ≤115 | ≥ 190 | | | |
| Hematocrit - Females | 0/ | ≤ 32 | ≥ 54 | | | |
| - Males | %0 | ≤ 3 7 | ≥ 60 | | | |
| Platelet count | x10 ⁹ cells/L | ≤ 75 | ≥ 700 | | | |
| | Blood Chem | iistry | | | | |
| Alanine aminotransferase (ALT) | | N/A | > 3 x ULN | | | |
| Aspartate aminotransferase (AST) | | N/A | > 3 x ULN | | | |
| Alkaline phosphatase (ALP) | | N/A | >3 x ULN | | | |
| Total bilirubin | | N/A | >2 x ULN | | | |
| Blood urea nitrogen (BUN) | | N/A | ≥10.7 mmol/L | | | |
| Creatinine | | N/A | ≥176.8 umol/L | | | |
| Sodium | mmol/L | ≤ 126 | ≥156 | | | |
| Potassium | mmol/L | ≤ 3 | ≥ 6 | | | |
| Chloride | mmol/L | ≤ 90 | ≥118 | | | |
| Bicarbonate | mmol/L | ≤ 16 | ≥ 35 | | | |

Table 1: Criteria for markedly abnormal laboratory

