At the Injection Day Visit (Visit 2, Day 0), subjects will undergo vitrectomy and iatrogenic retinal detachment as part of a sub-retinal injection procedure for administration of AAV8-RPGR in their study eye. To minimise inflammation resulting from surgery and/or vector/transgene, in Part I, all subjects will be given a 21-day course of oral corticosteroid (e.g., prednisolone/prednisone) that will start 2 days before the planned date of surgery (see Section 8.8 for details). In Part II, all subjects may be treated at the time of surgery with up to 1 mL of triamcinolone (40 mg/mL), administered via a deep sub-Tenon approach. Subjects will also be given a 9-week course of oral corticosteroid starting 3 days before surgery: 21 days at 60 mg, followed by 6 weeks of tapering doses. The dose regimen is adjusted for pediatric subjects treated in Part II (see Section 8.8).

Subjects in the untreated control group will receive study-visit telephone calls to monitor AEs/SAEs and review concomitant medications on Visit 2 (Day 0) and on Visits 3 and 4 (post-operative Days 1 and 7).

Subjects will be assessed for safety and efficacy throughout the study as indicated in the Schedule of Study Procedures (see Section 16.1). The safety evaluation will be based on the

occurrence of adverse event (AE) reporting (including DLTs); full ophthalmic examination (including indirect ophthalmoscopy, slit-lamp examination, intraocular pressure [IOP], anterior chamber and vitreous inflammation grading and lens opacities classification system III [LOCS III] cataract grading); fundus photography; vital signs; and laboratory assessments (including laboratory safety parameters, viral shedding and immunogenicity).

The efficacy evaluation will be based on microperimetry, BCVA, SD-OCT, fundus autofluorescence, visual fields (Octopus 900 specified in Part II only), contrast sensitivity, low luminance visual acuity (LLVA),

Any safety information collected as a result of the efficacy assessments (e.g., BCVA) will also be used in the overall safety evaluation, as applicable.

Subjects who develop cataracts may undergo cataract surgery if deemed clinically necessary; if surgery is performed, it should be carried out at least 4 weeks before their final visit.

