8.6. Study Masking

Part I of the study is open label.

Part II is double-masked (subject, surgeon, investigator/site team, and sponsor will be masked) to the assigned dose, and open-label with respect to the treatment procedure.

In Part II, ophthalmic assessments that will be used as efficacy endpoints (BCVA, LLVA, microperimetry, contrast sensitivity will be conducted by appropriately qualified assessors (see Table 1). For the immediate post-operative visits, masking of the assessors will not be viable as clinical signs of surgery will be apparent (i.e., redness, swelling). Therefore, unmasked assessors will perform all ophthalmic assessments at Visit 3 (Day 1), Visit 4 (Day 7), Visit 5 (Month 1), and Visit 5.9 (Month 2). From Visit 6 (Month 3) onwards, masked assessors will be used, as signs of surgery will have dissipated and it should not be possible clinically to differentiate between those subjects that have not undergone surgery, and those subjects that have undergone surgery and received active treatment. It is preferable that the same assessor who performed the efficacy endpoint assessments at Screening/Baseline also perform the assessments during the masked period from Month 3 to Month 12.

Table 1 Masked Assessments of Efficacy

Masked Assessments at Month 3, 6, 9 and 12 Post-Treatment with AAV8-RPGR

- Best-corrected visual acuity
- > Low-luminance visual acuity
- Microperimetry
- Contrast sensitivity

>

Subjects randomised to the untreated Control group will not be required to attend the site at Visit 2, 3 or 4. As the key purpose of Visit 2 is surgery, and Visit 3 and 4 are post-operative safety visits, there is limited utility in Control subjects attending. Therefore, to limit the study burden for Control subjects thereby potentially reducing the risk of subject withdrawal at this stage and reducing the possibility of further unmasking due to direct contact and communication with fellow participants, Control subjects are not scheduled to attend the clinic for study visits at these times.

To minimise bias further, masked assessors will not have access to the subject's medical records, source documentation or eCRF as data entries or notation (such as use of peri-

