9.3. Visit 3 (Day 1 Post-Operative Visit)

At Visit 3, the first post-operative visit, the following assessments will be performed:

- Blood pressure and pulse
- Full ophthalmic examination, including indirect ophthalmoscopy, a slit-lamp examination, IOP, anterior chamber and vitreous inflammation grading and LOCS III cataract grading
- ETDRS BCVA
- SD-OCT
- Viral shedding
- Immunogenicity sampling
- AE/SAE monitoring
- Review of concomitant medication, treatments, and procedures
- Corticosteroid compliance review¹
 - 1. Corticosteroid review is applicable only for treated subjects.

Where applicable, subjects will be reminded of the requirement to use barrier contraception or abstain from sexual intercourse for a period of 3 months from the time of treatment.

Subjects in the Control group will receive a study visit Telephone Call at the agreed upon date and time. Sites will conduct the following assessments during the telephone call:

- AE/SAE monitoring
- Review of concomitant medication, treatments, and procedures.

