9.4. Visit 4 (Day 7 Post-Operative Visit \pm 3 Days)

At Visit 4, the second post-operative visit, the following assessments will be performed:

- Blood pressure and pulse
- Collection of safety blood samples (hematology and clinical chemistry)
- Full ophthalmic examination, including indirect ophthalmoscopy, a slit-lamp examination, IOP, anterior chamber and vitreous inflammation grading and LOCS III cataract grading
- ETDRS BCVA
- SD-OCT
- Viral shedding
- Immunogenicity sampling
- AE/SAE monitoring
- Review of concomitant medication, treatments, and procedures
- Corticosteroid compliance review¹
 - 1. Corticosteroid review is applicable only for treated subjects.

Where applicable, subjects will be reminded of the requirement to use barrier contraception or abstain from sexual intercourse for a period of 3 months from the time of treatment. Subjects in the Control group will receive a study visit Telephone Call at the agreed upon date and time (\pm 3 days of Day 7). Sites will conduct the following assessments during the telephone call:

- AE/SAE monitoring
- Review of concomitant medication, treatments, and procedures.

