- b. Although the visit will still be considered out-of-window, if a subject in Part II is unable to attend the 12-month visit during the protocol-defined window, they should return to the site to complete this visit as soon as it is possible for them to do so. Delays will be identified as PDs on a case-by-case basis by the Sponsor based on information provided by the site; this will include but is not limited to scenarios such as site closure, travel bans, medical travel prohibitions, patient illness, etc.
- c. Visits 10 and 11 are for Part I subjects only

- d. Although the visit will still be considered out-of-window, if a subject in Part I is unable to attend the 24-month visit during the protocol-defined window, they should return to the site to complete this visit as soon as it is possible for them to do so. Delays will be identified as PDs on a case-by-case basis by the Sponsor based on information provided by the site; this will include but is not limited to scenarios such as site closure, travel bans, medical travel prohibitions, patient illness, etc.
- e. An early termination (ET) visit is to be performed if a subject discontinues at any time.
- f. If clinically indicated, subjects may need to return to the site for an unscheduled visit. At a minimum, the following assessments will be performed: full ophthalmic examination, BCVA, SD-OCT, microperimetry (if clinically feasible), fundus autofluorescence, AE/SAE monitoring, and concomitant medication, treatments, and procedures review
- g. Visits 2, 3, and 4 will be a telephone call only for subjects randomised to the control, untreated group. AE/SAE monitoring and concomitant medication, treatments, and procedures review will be assessed during the call.
- h. Includes hematology and clinical chemistry
- i. To be conducted only if unavailable at Visit 1
- j. Includes indirect ophthalmoscopy, slit lamp examination, IOP, anterior chamber and vitreous inflammation grading and LOCS III cataract grading
- k. Study eye only
- 1. Part I subjects will take 1 mg/kg/day prednisone/prednisolone for a total of 10 days (beginning 2 days before the vector injection, on the day of injection, and then for 7 days); followed by 0.5 mg/kg/day for 7 days; 0.25 mg/kg/day for 2 days; and 0.125 mg/kg/day for 2 days (21 days in total). Part II subjects in treated groups will be given a 9-week course of oral prednisone/prednisolone and instructed to start taking the drug 3 days before Visit 2. See Section 8.8.

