7.13.4 Dilated Ophthalmoscopy

Part I and Part II

The number and percentage of subjects within each category of each Dilated Ophthalmoscopy outcomes will be summarized by treatment groups, visits and eyes. Shift from baseline will also be evaluated. The shift for "Vitreous", "Macula", "Peripheral retina", "Choroid" and "Optic nerve" will be summarized from "Normal/Clinically insignificant abnormality", or "Clinically significant abnormality" at baseline to "Normal/Clinically insignificant abnormality", or "Clinically significant abnormality" at any visit post-baseline.

The shift for "Retinal tear(s)" and "Retinal detachment" will be summarized from "Absent", or "Present" at baseline to "Absent", or "Present" at any visit post-baseline.

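### Part II worst-value laboratory tables give operated subjects five chances to be flagged and controls four, and the retinal-detachment shift has no rule for the detachment made at surgery

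*SAP*

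**What the plan says.** **Laboratory rule.** SAP 7.13.10.1 defines the low/high shifts and the markedly abnormal counts cumulatively. For low values, "as long as one lab value is low this subject is regarded to have 'low' post-baseline for this lab parameter", and high values are treated alike. For the sponsor's own thresholds, "as long as one lab value is markedly abnormal this subject is counted to be markedly abnormal for this lab parameter". The section does not limit these tables to visits that every arm attends. SAP 7.3 sets baseline before treatment and analyses by nominal visit, so Days 1 and 7 are post-baseline.

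**Control schedule.** Protocol Table 3 (Section 16.1), footnote g: "Visits 2, 3, and 4 will be a telephone call only for subjects randomised to the control, untreated group". The calls cover adverse events and concomitant treatment only. Protocol 8.6 confirms it: "Subjects randomised to the untreated Control group will not be required to attend the site at Visit 2, 3 or 4".

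**Eye shifts.** SAP 7.13.4 tabulates retinal tears and retinal detachment from absent or present at baseline to "Absent', or 'Present' at any visit post-baseline". SAP 7.13.5 uses a similar phrase for slit-lamp findings.

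**Surgery.** Under Protocol 6.1, on the injection day "subjects will undergo vitrectomy and iatrogenic retinal detachment as part of a sub-retinal injection procedure".

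**Layout.** SAP 6.2 places treated and untreated Part II columns side by side in the safety tables. The Protocol synopsis says the untreated group is there to give a controlled comparison of both efficacy and safety.

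**The concern.** An 'ever abnormal' count rises with the number of looks. If one arm is looked at more often, its count rises even when the underlying rate is the same. Here the extra looks fall only in operated subjects and only in the first post-operative week.

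The extra laboratory draw is also not a typical one. Day 7 is the only scheduled post-baseline draw within the adult 60 mg steroid phase. A finding there enters the treated count with no control draw from the same week to set against it.

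The detachment shift has a separate problem of definition. Detaching the retina is a step of the procedure in every operated study eye. The SAP does not say whether a detachment still visible at Day 1 or Day 7 counts in the shift to 'present', or how it is to be kept apart from a detachment that appears later.

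What is at stake is how the between-arm safety tables are read. No efficacy result and no hypothesis test is involved.

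**Working it through.** **1. Schedule check.** Protocol 6.1 gives Part II 10 visits. Counting from Protocol 9.1 to 9.10: Visits 1, 2, 3, 4, 5, 5.9, 6, 7, 8 and 9, which is 10. The count agrees.

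**2. Scheduled post-baseline occasions by arm** (Table 3 and Protocol 9.3 to 9.10, less the control telephone visits):

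| Assessment | Operated | Untreated |
|---|---|---|
| Safety bloods | Day 7, Months 1, 2, 3, 12 = 5 | Months 1, 2, 3, 12 = 4 |
| Ophthalmoscopy, slit lamp | Days 1, 7, Months 1, 2, 3, 6, 9, 12 = 8 | Months 1, 2, 3, 6, 9, 12 = 6 |
| Fundus photography | Month 12 = 1 | Month 12 = 1 |

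No safety bloods are scheduled on Day 1, so the laboratory tables gain Day 7 only. Fundus photography is unaffected.

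**3. Effect of visit count alone.** The documents give no per-visit abnormality rates, so a common rate *p* is assumed over 1% to 10%, with independent visits. The chance of at least one flag in *k* visits is 1 − (1 − *p*)^*k*. The excess per 10 subjects is 10 times the difference; about 30 subjects randomised 1:1:1 is about 10 per arm.

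Laboratory tables, *k* = 5 v 4:

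| *p* | Operated | Untreated | Difference | Per 10 subjects | Ratio |
|---|---|---|---|---|---|
| 1% | 0.0490 | 0.0394 | 0.0096 | 0.1 | 1.24 |
| 5% | 0.2262 | 0.1855 | 0.0407 | 0.4 | 1.22 |
| 10% | 0.4095 | 0.3439 | 0.0656 | 0.7 | 1.19 |

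Eye examinations, *k* = 8 v 6, only if the shifts mean 'ever':

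| *p* | Operated | Untreated | Difference | Per 10 subjects | Ratio |
|---|---|---|---|---|---|
| 1% | 0.0773 | 0.0585 | 0.0188 | 0.2 | 1.32 |
| 5% | 0.3366 | 0.2649 | 0.0717 | 0.7 | 1.27 |
| 10% | 0.5695 | 0.4686 | 0.1009 | 1.0 | 1.22 |

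**4. Where Day 7 sits.** Protocol 8.8 has adults on 60 mg from Day −3 to Day 17. Visit 4 is Day 7 ± 3, so Days 4 to 10, inside that phase. The next draw, Month 1 ± 7 days, falls in the taper. If the Day 7 rate were 20% and every other draw 5% (assumed), operated subjects would reach 1 − 0.95^4 × 0.80 = 0.348 against 0.1855 in controls. An excess of that kind would be a real finding about the treatment regimen and should be reported. The pooled worst-value count, however, does not show which visit it came from.

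**5. Restricting to common visits.** From Month 1 to Month 12 the counts are 4 v 4 draws and 6 v 6 examinations, so the ratio due to visit count is 1.00.

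**6. Detachment.** Set side by side, Protocol 6.1 and 8.4 create a detachment in each operated eye, and SAP 7.13.4 tabulates detachment after baseline. No sentence in either document links the two.

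**The case against.** The case for leaving the plan alone has several sound parts.

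- *Other outputs show timing.* SAP 7.13.4 and 7.13.5 also tabulate findings by visit and eye. SAP 7.13.10.1 summarises laboratory values at each visit and lists them by visit. SAP 7.13.1 separates events by eye and by relation to drug or procedure. A reader might infer that a later detachment or laboratory abnormality could not be told from an early one. These outputs contradict that.
- *The eye shifts can be read by visit.* Protocol 12.7.2 summarises ophthalmoscopy and slit-lamp findings by visit and eye. On that reading the 8 v 6 imbalance disappears and a Day 1 detachment sits in the Day 1 rows. The laboratory rule does not allow such a reading.
- *The size is modest and assumed.* The per-draw rates are not from the documents. Repeat values in one person are usually positively correlated, which shrinks the excess.
- *Safety is descriptive.* Protocol 12.7 plans no safety testing. The Part II safety endpoint is the incidence of treatment-emergent events, and controls are telephoned about adverse events on Days 0, 1 and 7.
- *The acute window matters.* In a first-in-human surgical trial, dropping Days 1 and 7 from the tables would hide the period of greatest interest.

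All of this stands, and it limits the point without removing it. No by-visit output corrects the cumulative laboratory table, and no rule for the surgical detachment appears anywhere.

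Two further inferences should be resisted. One is that nearly every treated eye will shift to 'present': the documents do not say how long the surgical detachment lasts or how it is to be recorded, so it can count, not that it will. The other is that Day 7 is a steroid peak: the adult dose is level from Day −3 to Day 17 and treatment runs to Day 59, so common-visit tables would still contain steroid effects.

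**Conclusion.** The point holds for the laboratory tables without qualification as to reading: five scheduled draws against four under a one-value-is-enough rule. The excess from visit count alone is 0.1 to 0.7 of a subject per 10 at per-draw rates of 1% to 10%, assuming equal rates, independent draws and full attendance at scheduled visits. It is smaller with positive within-subject correlation. It would be larger if Day 7 has a higher rate, but that part would be a genuine effect.

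For ophthalmoscopy and slit lamp the imbalance (0.2 to 1.0 of a subject per 10 on the same assumptions) is conditional on 'any' meaning 'ever'. The missing rule for the surgical detachment does not depend on that reading.

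The consequence is a descriptive safety comparison that is not like for like as written. It is worth correcting because the untreated arm was added partly for that comparison. It does not invalidate the safety reporting.

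**What to change.** In SAP 7.13.4, 7.13.5 and 7.13.10.1:

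1. Keep the all-visit worst-value and shift tables, so that the acute post-operative period stays in the report.
2. For the treated v untreated comparison, add worst-value and shift tables restricted to visits both groups attend, Month 1 to Month 12.
3. Show Day 1 and Day 7 eye findings and Day 7 laboratory findings for operated subjects in a separate table.
4. In 7.13.4, give detachment seen at Day 1 or Day 7 its own rows, apart from detachment first seen from Month 1 onward. Do not label the early rows as procedural by default, since that could pass off an unreported complication as expected.
5. State in 7.13.4 and 7.13.5 whether the shift is to each visit or to the worst of all visits.

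The cost is a programming filter, a few extra tables and some sentences of text. No safety data are removed. The restricted tables will not remove steroid effects from Month 1 onward and should not be described as doing so.

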7.13.10.2 Viral Shedding

If a suitable sample is developed and validated upon data base lock, the following analyses will be performed.

Presence or absence of AAV8 DNA in different bodily fluids (tears [each eye], saliva, blood, and urine) will be determined by quantitative polymerase chain reaction (qPCR) at screening and subsequent visits. For each sample type, the number and percentage of positive, negative, and below level of quantification (BLQ) samples will be summarized by treatment groups and visits. In addition, listings of individual viral shedding results will be provided.

7.13.10.3 Immunogenicity

The immunogenicity analyses will be based on subjects who have at least one post-surgery sample evaluable for immunogenicity from safety analysis set.

Immunogenicity encompasses neutralizing antibody (NAb) assay, enzyme-linked immunospot (ELISpot) assay and anti-drug antibody (ADA) assay.

NAb

If a suitable NAb assay is developed and validated upon data base lock, the following analyses will be performed.

Serum NAb levels at screening and subsequent visits will be reported as the reciprocal of the highest fold of dilution (titer) needed to rid the sample of neutralizing activity against an AAV8 reporter virus. The results will be reported as "<1", ">15,000", and continuous values between 1 and 15,000. Results of "<1" are regarded as negative, and results of ">1" are regarded as positive.

The baseline value for NAb is defined as the last available value prior to surgery of the treated eye. For subjects without any assessments prior to surgery of the treated eye, Day 1 sample will be used as baseline. If both prior to surgery and Day 1 assessments are not available, NAb samples at baseline will be regarded as missing.

Pre-existing immunoreactivity is defined as a positive NAb assay response at baseline. Treatment-emergent positive is defined as any post-treatment positive NAb assay response when the baseline NAb result is negative. Treatment-boosted is defined as any posttreatment positive NAb assay response greater than or equal to a 4-fold change over baseline titer level, when baseline NAb assay is positive.

The number and percentage of subjects with positive and negative NAb assay will be summarized by treatment groups and visits. The number and percentage of subjects with preexisting immunoreactivity, treatment emergent positive, treatment-boosted, and negative at both screening and post-baseline will be also summarized by treatment groups. Listing of individual NAb result will be provided.

To determine the relationship between NAb and post-treatment ocular inflammation related adverse events, the NAb status (pre-existing immunoreactivity, treatment emergent positive, treatment-boosted, and negative at both screening and post-baseline) will be summarized for subjects who experience ocular inflammation adverse events post treatment. The ocular inflammation adverse event is defined from the custom search strategy. The impact of NAb status on other safety/efficacy may be further evaluated when sufficient data are obtained.

ELISpot

If a suitable ELISpot assay is developed and validated upon data base lock, the following analyses will be performed.

Cellular immunity mediated by cytotoxic T lymphocytes (CTL) will be evaluated by Interferon-gamma (IFN- γ) ELISpot assay of peripheral blood mononuclear cells (PBMC). Cellular immunity will be evaluated at baseline and post-baseline visits according to the protocol's schedule of events and is reported positive or negative by peptide pool stimulation and as spot forming units (SFU) per 10⁶ PBMC.

The number of subjects and percentage with positive and negative ELISpot will be summarized by treatment groups and visits. A listing of individual ELISpot data will be provided. The potential relationship between ELISpot and safety/efficacy may be further evaluated when sufficient data are available.

Anti-Drug Antibody (ADA)

An assay for measuring anti-RPGR protein antibody is under development. If a suitable assay is developed and validated upon data base lock, the following analyses will be performed.

The baseline value for ADA is defined as the last available value prior to surgery of the treated eye. For subjects without any assessments prior to surgery of the treated eye, Day 1 sample will be used as baseline. If both prior to surgery and Day 1 assessments are not available, ADA samples at baseline will be regarded as missing.

Pre-existing immunoreactivity is defined as a positive ADA assay response at baseline. Treatment-emergent positive is defined as any post-treatment positive ADA assay response when the baseline ADA assay is negative. Treatment-boosted is defined as any post-treatment positive ADA assay response that is greater than or equal to a 4-fold change over baseline titer level, when baseline ADA assay is positive.

The number and percentage of subjects with positive or negative ADA assay at each visit will be summarized. The number and percentage of subjects with pre-existing immunoreactivity, treatment-emergent positive, treatment-boosted, and negative at both screening and post-baseline will be summarized by treatment groups. Listings of ADA positivity/negative status and titers will be presented by subject and time point.

